#### **9.4.4 Pregnancy test**

A serum pregnancy test ( $\beta$ -hCG) will be performed at run-in (V1) in women of childbearing potential, and a urine dipstick pregnancy test will be performed at V2 prior to randomization and every 4 weeks. A negative result must be obtained at V1 and V2 prior to randomization. In case of positive urinary test the study treatment will be withheld and a serum pregnancy test to confirm the pregnancy should be performed as soon as possible. Pregnancy will lead to definitive treatment discontinuation in all cases.

#### **9.4.5 Vital signs**

Vital signs include: blood pressure (mmHg), heart rate (beats per minute), respiration rate (breaths per minute), body temperature (degrees Celsius) and body weight (kg). Height (cm) will be measured on V1 only. Vital signs will be measured in the sitting position using the same Arm (preferably) at each visit, and will be measured prior to receiving IMP at the clinic visits.

#### **9.4.5.1 Physical examination**

Physical examinations will include an assessment of general appearance, skin, eyes, ear/nose/throat, heart, chest, abdomen, reflexes, lymph nodes, spine, and extremities. All deviations from normal will be recorded, including those attributable to the patient's disease.

#### **9.4.6 Electrocardiogram variables**

A standard 12-lead electrocardiogram (ECG) will be performed at the sites at the time points noted in the Study Flowchart ([Section 1.2](#)) to monitor any potential abnormality. In case of an abnormal ECG finding, the Investigator should enter details into the e-CRF. At V2, the Investigator should use their medical judgment to consider whether the patient is eligible for the study.

### **9.5 OTHER ENDPOINTS**

#### **9.5.1 Functional dupilumab concentration and anti-drug antibodies in serum**

##### **9.5.1.1 Sampling time**

Predose blood samples will be collected for determination of functional dupilumab (pharmacokinetics, or PK) in serum and anti-dupilumab antibodies at timepoints designated in the study flow chart (see [Section 1.2](#)). The date of collection should be recorded in the patient e-CRF. The date and time also will be collected on the central laboratory requisition form and entered into the database through data transfers from the central laboratory.

In the event of any SAE or any AESI of anaphylactic reactions or systemic allergic reactions that are related to IMP and require treatment, or severe injection site reaction lasting longer than 24 hours, samples will be collected near the onset and resolution of the event for any additional analysis if required or for archival purposes. An unscheduled systemic drug concentration page in the e-CRF must be completed as well.

Patients who are ADA positive at their last study visit (early termination or planned end of study [EOS]), may be asked to return to the clinic to have additional ADA samples collected for analysis based on the overall clinical presentation at the time of discontinuation.

##### **9.5.1.2 Handling procedures**

Special procedures for collection, storage, and shipping of serum are described in separate operational manuals. An overview of handling procedures for samples used in the determination of functional dupilumab serum concentration and anti-drug antibodies is provided in [Table 2](#).

**Table 2 - Summary of handling procedures for SAR231893 (dupilumab)**

Sample type	Functional dupilumab serum concentration	Anti-dupilumab antibody
Matrix	Serum	Serum
Blood sample volume	5 mL	5 mL
Anticoagulant	None	None
Blood handling procedures	See Operational Manual	See Operational Manual
Serum aliquot split	Two aliquots	Two aliquots
Storage conditions	<6 months: below -20°C	<6 months: below -20°C
Serum shipment condition	≥6 months: below -80°C (preferred) In dry ice	≥6 months: below -80°C (preferred) In dry ice

### 9.5.1.3 *Bioanalytical methods*

Serum samples will be assayed using validated methods as described in [Table 3](#).

**Table 3 - Summary of bioanalytical methods for dupilumab and anti-dupilumab antibody**

Analyte	Functional dupilumab concentration	Anti-dupilumab antibody
Matrix	Serum	Serum
Analytical technique	ELISA	Electrochemiluminescence

### 9.5.1.4 *Functional dupilumab concentration and anti-drug antibody measurement and samples*

Pre-dose functional dupilumab concentrations in serum at V2 (Day 1), dupilumab trough concentrations at Week 2, Week 4, Week 16, Week 24, Week 40, Week 52/EOT Visit, and post-treatment at Week 64/EOS Visit will be provided.

Anti-dupilumab antibody status (negative or titer value) will be provided for samples collected at timepoints as specified in the Study Flow Chart.

Patients who are ADA positive at their last study visit (early termination or planned EOS), will be considered for follow-up based on the overall clinical presentation at that time.

Unused samples collected for drug concentration or ADA analyses may be used for exploratory analyses if the specific Future Use of Samples Informed Consent is signed (see [Section 9.6](#)).

## 9.5.2 Pharmacodynamics

Several biomarkers related to CRSwNP and Th2 polarization will be assessed for their value in predicting therapeutic response and/or in documenting the time course of drug response.

Patients, Investigators and site personnel will not have access to assay results for total IgE, TARC, periostin, and eotaxin-3 while the study is ongoing, as the related data are not essential for patient care and have the potential for unblinding the study treatments.

Sample collection will be performed as per the study flow chart ([Section 1.2](#)) and assay methodologies are briefly summarized below. In general, duplicate aliquots of each sample for pharmacodynamic biomarkers should be stored to assure generation of a complete set of assay results. More detailed information on the collection, handling, transport and preservation of samples (eg, minimum volumes required for blood collection and for aliquots for each biomarker assay) will be provided in a separate laboratory manual.

### 9.5.2.1 Serum biomarkers

Total IgE will be measured using quantitative methods (eg, ImmunoCAP® FEIA), approved for diagnostic testing.

Thymus and activation-regulated chemokine will be assayed with a validated enzyme immunoassay (eg, Human TARC Quantikine ELISA kit; R&D Systems).

Concentrations of periostin will be assayed with a validated immunoassay.

### 9.5.2.2 Plasma biomarkers

Eotaxin-3 will be measured in heparinized plasma with a validated enzyme immunoassay.

### 9.5.2.3 Urine biomarkers

Leukotriene E4 and a metabolite of prostaglandin D2 (PGDM) will be measured in morning spot urine samples using validated quantitative assays. Assay results will be reported per mg of creatinine.

### 9.5.2.4

[REDACTED]

[REDACTED]

**9.5.3** [REDACTED]

[REDACTED]

[REDACTED]

[REDACTED]

[REDACTED]

[REDACTED]

[REDACTED]

[REDACTED]

## 9.6 FUTURE USE OF SAMPLES

Not all of the samples collected during this study may be required for the tests planned in this clinical trial. For patients who have consented to it, the samples that are archived, unused or left over after planned testing may be used for additional research purposes [REDACTED]

[REDACTED] For patients who have consented to it, archival blood samples will be collected at the visit specified in the study flow chart, 10 mL each, will be collected into a dry, red topped tube with clotting activator (or into smaller tubes of equivalent total volume) kept at room temperature for 30 minutes and then centrifuged at approximately 1500 g for 10 minutes at room temperature. The serum will then be transferred, in equal portions, into 3 storage tubes, which will be immediately capped and frozen in an upright position at -20°C or colder.

These archived serum samples, and any residual or leftover serum, plasma or blood remaining from planned laboratory work, may be used for research purposes related to airway disease, response to dupilumab treatment, additional drug safety assessments or development and validation of bioassay methods beyond those defined in the present protocol.

These samples will remain labelled with the same identifiers as the ones used during the study (ie, Subject ID, Sample ID). They will be transferred to a Sanofi site (or a subcontractor site) which can be located outside of the country where the study is conducted. The Sponsor has included safeguards for protecting patient confidentiality and personal data (see [Section 14.3](#) and [Section 14.5](#)).

## 9.7 APPROPRIATENESS OF MEASUREMENTS

Refer to [Section 4.4.1](#) for rationale on the co-primary endpoints. The proposed study design and endpoints will answer important clinical questions about the efficacy on symptoms and objective signs of the disease and the effect of dupilumab on reduction of SCS rescue therapy and surgery, which are the most relevant clinical practice assessments and reflect current standard of care.

## 10 STUDY PROCEDURES

Medical history should be recorded consistent with Good Clinical and local practice. This would typically include atopic medical history (including asthma history, hypersensitivity to aspirin or NSAIDs, NERD, allergy/atopy history), history of surgeries, concomitant medications, etc.

### 10.1 VISIT SCHEDULE

This section describes how the visits are carried out, in chronological order (according to the flow chart [Section 1.2](#) and identical to the order shown in the e-CRF):

The clinical trial consists of three periods, using an add-on therapy approach to INCS:

- Run-in Period (28 days+/- 3 days; V1).
- Randomized treatment period (up to 52 weeks +/- 3 days; Visits 2-10).
- Post-treatment Period (12 weeks; +/- 3 days V11).

The study visits occur on the planned dates (relative to the first injection), as scheduled. The visit schedule should be adhered to within the  $\pm 3$  day visit window.

If a patient is prematurely discontinued from treatment, every attempt should be made for the patient to return to the study site as soon as possible after last IMP administration to perform all assessments planned at the EOT visit and patients will be asked and encouraged to return to the study site for the visit scheduled as described in [Section 10.3.1](#) (early discontinuation) for a 12-week follow up.

Prior to all screening assessments, after discussion of participation in the study, the written consent form [REDACTED] must be signed and dated (see [Section 12.2](#)). At selected sites, requirements for collection of samples for a nasal biomarkers substudy will be included in a separate written informed consent.

Although the screening assessments for this study are grouped under the heading of a single visit in this protocol, it is possible for them to be performed over more than 1 site visit if necessary, as long as the run-in period window prior to Day 1 (V2) is respected. These patients do not need to sign a new consent form and be allocated a new patient number within this same window.

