STUDY DESIGN	
General design
 
Multinational, multicenter, randomized, double-blind, placebo-controlled, parallel group study comparing the efficacy of dupilumab compared to placebo, in patients with bilateral NP treated with intranasal corticosteroids (INCS).
 
Study periods
 
The clinical trial consists of 3 periods:
 
Run-in period (4 weeks +/-3 days):
 
All patients will enter a run-in period of 4 weeks receiving MFNS of 2 actuations (50 µg/actuation) in each nostril twice daily (BID), total daily dose of 400 µg, starting at Visit 1 (V1), unless the patients are unable to tolerate or there is a specific regulatory requirement preventing use of this dose in which case, they can stay on a lower dose regimen (200 µg once daily) of MFNS.
 
Randomized treatment period (up to 52 weeks +/-3 days):
 
Patients will be randomized to one of the following treatments:
 

• Arm A: dupilumab 300 mg subcutaneous (SC) q2w until Week 52.

• Arm B: dupilumab 300 mg SC q2w until Week 24, then 300 mg q4w until Week 52.

• Arm C: placebo matching dupilumab SC q2w administration until Week 52.

 
All patients will continue on the stable dose of MFNS used during the run-in period except if dose is changed due to adverse event (AE).
 
Rescue:
 
During the study treatment period and off treatment follow-up, based on clinical evaluation, in case of worsening of signs and/or symptoms requiring medical intervention, the Investigator may consider rescue treatment with:
 

• Nasal lavage with saline and/or systemic antibiotics (up to 2 weeks in case of acute infection)

• Short course oral corticosteroids (OCS) (prednisone or prednisolone)

• Sino-nasal surgery for nasal polyps (based on previous observations, 8 weeks of IMP treatment is recommended prior to surgery to allow onset of treatment effect).

 
Patients receiving rescue treatment other than surgery during the study should continue on study drug unless the Investigator decides to withdraw the study treatment (see Section 8.2.2). Before starting treatment with SCS patients should come to the study site for the clinical assessments including endoscopy and PROs.
 
For patients who undergo or are planned for surgery for NP the Investigator may decide to continue IMP up to the time of surgery or end of treatment whichever date comes first (see Section 9.2.1.5 for details). At the time of surgery patients will be permanently discontinued from study treatment and assessed as soon as possible using the procedures described in Section 10.3.1.
 
Post treatment period (12 weeks +/- 3 days):
 
After completing 52 weeks of treatment with the investigational medicinal product (IMP) (or following early discontinuation of IMP or discontinuation from the study), patients will be instructed to:
 
Return to the study site for such evaluations as pharmacokinetic (PK) and ADA, physical examination, nasal peak inspiratory flow (NPIF), University of Pennsylvania Smell Identification Test (UPSIT), NPS, PROs (SNOT-22, VAS),

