### 10.3.1 Permanent treatment discontinuation with investigational medicinal product(s)

Permanent treatment discontinuation is any treatment discontinuation associated with the definitive decision from the Investigator or the patient not to re-expose the patient to the IMP at any time.

Patients who discontinue treatment permanently during the treatment period will be assessed as soon as possible using all procedures normally planned for the End-of-treatment Visit with the exception of CT Scan. Patients who discontinue early during the post-treatment period will be assessed as soon as possible using all procedures normally planned for the end-of-study (EOS) Visit.

For patients in whom the surgery date is scheduled after the planned end of study, a follow up contact(s) should be performed around the time of planned surgery to document the surgery date. Surgery data will be collected only until e-CRF Closure and EOS will not be delayed.

Patients will also be instructed to:

- Return to the study site for evaluations of NPS, SNOT-22, at:
  - Week 24, Week 52: If the ETD visit occurred between Week 0-Week 16,
  - Week 52: If the ETD visit occurred between >Week 16-Week 40,
  - Week 64 (EOS): If the ETD visit occurred between >Week 40-Week 52.
- Return and have a CT Scan performed as scheduled at Week 24 and 52.

Patients who discontinue prior to week 40 will have the following assessed through week 52, patients who discontinue after week 40 will have the following assessed through week 64:

- Perform PK and ADA sampling at the initially scheduled visits for these assessments
- Continue to complete the e-diary for nasal congestion, loss of smell daily symptom and anterior/posterior rhinorrhea evaluation
- Continue on MFNS stable dose but patients are not required to complete the INCS use daily in the e-diary after ETD.
- Advise patients with comorbid atopic conditions (such as asthma) not to adjust their treatment without consultation with their physicians.
- Report any AE up to the last scheduled visit (Week 52 or Week 64 depending on the discontinuation date).
- Contact the Investigator during the post treatment period up to the EOS visit if the symptoms worsen requiring medical attention.

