2.4.4.1 Analysis of primary efficacy endpoint(s)

Co-primary efficacy variables

The co-primary efficacy variables are: change from baseline in NC and in NPS (change from baseline in NC, NPS and LMK for Japan) at Week 24 assessed for dupilumab 300 mg q2w (pooled A and B arms) versus placebo, respectively.

The following null hypothesis and alternative will be tested for pooled dupilumab arms against placebo:

- H0: No treatment difference between the dupilumab dose regimen and placebo.
- H1: There is a treatment difference between the dupilumab dose regimen and placebo

Primary statistical model (ITT analysis)

Each of the 2 co-primary efficacy endpoints (3 co-primary efficacy endpoints for Japan) will be analyzed using a hybrid method of the worst-observation carried forward (WOCF) and multiple imputation. Data collected after treatment discontinuation will be included in the analysis. With this approach, for patients who undergo surgery for NP or receive SCS for any reason, data collected postsurgery (actual date) or post SCS will be set to missing, and the worst postbaseline value on or before the time of surgery or SCS will be used to impute missing Week 24 value (for patients whose postbaseline values are all missing, the baseline will be used to impute). For patients who discontinue the treatment without being rescued by surgery or receiving SCS, a multiple imputation approach will be used to impute missing Week 24 value, and this multiple imputation will use all patients who have not been rescued by surgery or receiving SCS at Week 24. Each of the imputed complete data will be analyzed by fitting an ANCOVA model with the baseline value of the corresponding co-primary endpoint, treatment group, asthma/NERD status, prior surgery history, and regions as covariates. Statistical inference obtained from all imputed data will be combined using Rubin's rule. Descriptive statistics including number of patients, mean, standard error, and least squares (LS) means will be provided. In addition, difference in LS means and the corresponding 95% confidence intervals (CI) will be provided along with the p-values.

Imputation and analysis model will be built with the following sample SAS code:

1. 40 datasets with a monotone missing pattern will be obtained, induced by Markov Chain Monte Carlo (MCMC) method on patients who have not been rescued by surgery or receiving SCS at Week 24.

```
proc mi data=dat_etd seed=14280 nimpute=40 out=dat_mc;  

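### Protocol 10.1 and the synopsis attach a 12-week follow-up to early discontinuers that Section 10.3.1 does not contain; applied literally, it would lose Week 24 data for stops before about Week 8 and Week 52 data for anyone stopping by Week 24

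*Protocol*

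**What the plan says.** **Protocol 10.1 (Visit schedule).** A patient who stops treatment prematurely has the end-of-treatment assessments and is then encouraged to return as described in Section 10.3.1, with the qualifier "early discontinuation) for a 12-week follow up".

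**Protocol synopsis, post-treatment period (12 weeks ± 3 days).** The period covers patients who complete 52 weeks and also those in the parenthesis "or following early discontinuation of IMP or discontinuation from the study), patients will be instructed to" return for NPS, patient-reported outcomes, PK and ADA, and to continue the e-diary. The same block ends by referring early discontinuation of IMP to Section 10.3.1.

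**Protocol 10.3.1.** No 12-week period appears. The NPS and SNOT-22 returns depend on when the early-termination visit took place. For the earliest stops the entry reads "Week 24, Week 52: If the ETD visit occurred between Week 0-Week 16". A termination visit later than Week 16 but no later than Week 40 leads to a single return, at Week 52. One later than Week 40 leads to a single return, at Week 64.

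CT is kept at Weeks 24 and 52. For the e-diary, PK/ADA and AE reporting the rule is "Patients who discontinue prior to week 40 will have the following assessed through week 52", and through Week 64 for later stops.

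**Protocol 10.3.4.** Follow-up runs at least to the scheduled date of study completion.

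**SAP 2.4.4.1.** For the co-primary analysis: "Data collected after treatment discontinuation will be included in the analysis". SAP 2.4.4.2 analyses NPS, NC and SNOT-22 at Week 52 in the same way, and SAP 2.4.4.3 puts the Arm A versus placebo comparisons for all three in the alpha-controlled hierarchy.

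**The concern.** The same patients have two different ends of follow-up. Under the 12-week wording, a patient who stops at Week 4 is finished at Week 16. Under 10.3.1 the patient returns at Weeks 24 and 52. Section 10.1 cites 10.3.1 as its source, yet the cited section does not contain the number.

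This is an instruction that sites act on. Including off-treatment data in the analysis works only if sites collect those data. Where they are missing and the patient has had neither systemic corticosteroids nor surgery, SAP 2.4.4.1 fills the value by multiple imputation from patients not rescued by that visit. An off-treatment value that 10.3.1 would have supplied is then replaced by a modelled one.

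**Working it through.** **Inputs**
- Day number of Week w: 7w + 1, so Week 24 is Day 169 and Week 52 is Day 365 (flow chart).
- 12 weeks = 84 days. The protocol does not say when the 12 weeks start; they are first counted from the stop.
- Week 24 windows: endoscopy Days 141–224 (SAP Table 4); NC diary average Days 142–169 (SAP Table 2).
- Week 52 windows: NPS Days 323–406 and SNOT-22 after Day 322 (Table 4); NC Days 338–365 (Table 2).

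**The plan's own figure.** Protocol 6.2.1 gives about 68 weeks of participation for patients who complete treatment and follow-up: 4 + 52 + 12 = 68. The 12 weeks fit completers.

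**The two rules side by side**

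| Stop | End of 12 weeks | NPS/SNOT-22 returns in 10.3.1 | Shortfall to last return |
|---|---|---|---|
| Week 4 (Day 29) | Week 16 (Day 113) | Weeks 24, 52 | 36 weeks |
| Week 8 (Day 57) | Week 20 (Day 141) | Weeks 24, 52 | 32 weeks |
| Week 12 (Day 85) | Week 24 (Day 169) | Weeks 24, 52 | 28 weeks |
| Week 24 (Day 169) | Week 36 (Day 253) | Week 52 | 16 weeks |
| Week 40 (Day 281) | Week 52 (Day 365) | Week 52 | 0 |
| Week 50 (Day 351) | Week 62 (Day 435) | Week 64 | 2 weeks |

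Follow-up under 10.3.1 lasts 52 − w weeks for stops up to Week 40 and 64 − w weeks after that. It equals 12 only at w = 40 or w = 52.

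**Week 24, stop on Day D, last contact on Day D + 84**
- Nominal visit missed if D + 84 < 169, so D < 85 (before Week 12).
- No end-of-follow-up endoscopy in the window if D + 84 < 141, so D < 57 (before Week 8). This assumes an endoscopy at the end of the 12 weeks that counts as a scheduled measurement.
- No NC diary day in the window if D + 84 < 142, so D < 58. From there, at most D − 57 of the 28 days are covered: 1 day at D = 58, 27 at D = 84, all 28 at D = 85.

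**Week 52.** A stop on Day 169 ends on 169 + 84 = Day 253. That is before Day 323 (NPS and SNOT-22) and Day 338 (NC), so no patient stopping by Week 24 reaches any Week 52 window.

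**Other starting point.** If the 12 weeks begin 14 days after the last dose (the SAP 2.1.4 residual treatment epoch, last dose + 98 days), the cut-offs for the last dose become Day 71 (169 − 98), Day 43 (141 − 98) and Day 44 (142 − 98). A last dose on Day 169 then ends on Day 267, still before every Week 52 window.

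**What remains under 10.3.1.** A patient stopping after Week 16 and before Week 24 has NPS at the early-termination visit and next at Week 52. An early-termination endoscopy on Days 114–140 falls in the Week 16 window (Days 85–140), so there is no Week 24 NPS. NC is not affected, because the e-diary continues.

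**The case against.** The strongest reply is that the governing rule is not in doubt. The sentence in 10.1 itself sends the reader to 10.3.1. So do the end of the synopsis block, the flow-chart notes on early discontinuation and surgery, and Sections 8.2.2, 9.2.1.5, 10.3.4 and 10.4.3. Only 10.3.1 lists returns by stopping week. The 12-week phrase then reads as leftover text. This stands: 10.3.1 is the intended rule, and the design already collects the needed data. It does not remove the problem, because 10.1 and the synopsis still give sites a duration that the cited section contradicts.

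Two stronger readings are tempting, and the documents support neither.

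- **A reader might infer that everyone stopping before Week 12 loses the co-primary assessment.** That is true only of the nominal Day 169 visit. The Table 4 window lets an endoscopy at the end of 12 weeks count for stops from Day 57, and NC is partly observed for stops from Day 58.
- **A reader might take the 25% dropout allowance as early stops spread over 24 weeks and compute a bias.** Nothing says what the allowance consists of or when stops occur. Patients given systemic corticosteroids or surgery are handled by worst observation carried forward, not imputation. The imputation model also uses each patient's own earlier changes. Protocol 4.4.2 reports a persistent off-treatment effect in the phase 2 study, so a large loss of effect cannot simply be assumed. The SAP also plans copy-increment-from-placebo and tipping-point analyses.

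**Conclusion.** The contradiction is real and worth correcting, because a literal reading removes data that the analyses state they include. Its reach, with 12 weeks counted from the stop, is:

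- **Stops before about Week 8:** neither Week 24 NC nor an end-of-follow-up NPS in the SAP windows.
- **Stops from about Week 8 to Week 12:** partial Week 24 NC only; NPS can still fall in the window.
- **Stops by Week 24:** no Week 52 NPS, NC or SNOT-22. This is the clearest loss, since no window recovers it and these endpoints are in the testing hierarchy for Arm A.

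The Week 24 cut-offs move about two weeks earlier if the period starts 14 days after the last dose. All of this is conditional on a site following the 12-week wording instead of 10.3.1. How many patients would be affected, and by how much the estimates would shift, cannot be derived from the documents.

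**What to change.** 1. In Protocol 10.1, delete the 12-week phrase so that the sentence points only to Section 10.3.1.
2. In the synopsis, limit the 12-week post-treatment period to patients who complete treatment, and state that early discontinuers follow 10.3.1.

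The cost is two wording changes in an amendment. No visits are added, because 10.3.1 already schedules them.

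These edits do not secure Week 24 NPS for patients who stop after Week 16 and before Week 24, for whom 10.3.1 lists an NPS return only at Week 52. The sponsor should decide in the same amendment whether to add a Week 24 endoscopy for them. That would be a real addition to the schedule, or else the missing value should be acknowledged as left to imputation.
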